6.8 Data Collection Sources

Formative Work: The focus group guide will be organized based on the constructs of a safety planning intervention (e.g., potential warnings signs related to emotional distress, coping strategies, and resources for seeking support).

Pilot Study: We will assess the user experiences (e.g., acceptability and usability) as well as feasibility of delivering protocols of the digital game. From our playtesting focus groups (i.e.,

where we obtained feedback to finalize the prototype), will modify two approaches: the think-aloud method and cognitive interviewing. The think-aloud method and cognitive interviewing are mainly used to analyze how human participants perform and interact with a prototype or interface of a product. By conducting either of these methods when testing the usability of a product, issues with the prototype can be identified and fixed. The think-aloud method specifically requires participants to speak aloud their thought processes and ideas as they perform a specific task or solve a problem. Sometimes the method is carried out one-on-one with a participant and a research/note taker, while other times video recordings can be used.² By having the participants verbally articulate their thought process, the researchers will be able to gain insight on potential issues or complications with the game design and/or playtesting process. In context of the Pilot Study, aspects from the think aloud method and cognitive interviewing will be applied simultaneously in our post-gameplay focus group, which allows for feedback and discussion on the content of the game, as well as the process through which the game is being presented for playtesting. Along with the use of these methods to gather feedback on the digital game, quantitative measures are also being gathered through the use of the **User Engagement Scale- Short Form (UES-Short Form)**, and **Acceptability of Intervention Measure (AIM) as examples**. These scales along with qualitative data collection and observation will assess the usability, acceptability, and feasibility of the game.

The User Engagement Scale-Short Form (UES-Short Form) is a validated, 12-item self-report measure that assesses six domains of engagement where responses are measured on a 5-point Likert scale where 1= strongly disagree and 5= strongly agree.

The Acceptability of Intervention Measure (AIM) is a validated, 4-item self-report measure of perceived acceptability where responses are measured on a 5-point Likert scale where 1 = completely disagree and 5= completely agree.

Lastly, feasibility of delivering protocols and procedures will be measures through observation of modifications to conduct study, duration of gameplay, and reasons if did not finish game to end. Participants will also answer qualitative questions (e.g. does the game work? can the game be implemented in schools?) that will be developed by the study team. By gathering both qualitative and quantitative data and feedback on the protocol design of the digital game, appropriate revisions can be made to future versions of the game.

We will also explore proximal outcomes such as but not limited to adolescent well-being, intentions to use a safety planning intervention, coping strategies, substance misuse in last 30 days, and associated risk factors related to suicidal risk (e.g., hopelessness, impulsivity, etc.). Our specific measures and proximal outcomes are outlined below:

Coping Strategies

Change in coping strategies will be assessed using the brief COPE scale at baseline and 3-months follow-up. Brief COPE adaptive and maladaptive subscales are validated, 28- item, 4-point self-report measures. Brief COPE measures assess 14 conceptually different coping reactions. Responses are measured on a 4-point likert scale where 1= I haven't been doing this at all and 5= I've been doing this a lot.

Mindfulness

To assess facets of mindfulness, we will utilize The Five Facet Mindfulness Questionnaire (FFMQ). The FFMQ is a validated, 15-item self-report measure that assesses facets of mindfulness. Responses are measured on a 5 point-likert scale where 1= never or very rarely true, and 5= very often or always true.

Emotion Regulation

Emotion regulation will be assessed using the State-Difficulties in Emotion Regulation (S-DERS) scale, a 21-item self-report measure. Responses are measured on a 5-point likert scale where 1= almost never and 5= almost always.

Adolescent Well-Being

Adolescent well-being will be measured using The Adolescent Well-Being assessment, which is a validated, 16-item school-based, self-report measure with 11-items focused on well-being, and 5-items focused on student demographics.

Intentions to Use a Safety Plan

Intentions to use a safety plan is a 7-item measure adapted from Addis et al., 2013. Responses are measured on a 5-point likert scale where 1= strongly disagree and 5= strongly agree.

Knowledge about the Safety Planning

Participants will complete surveys through a secured, data management system (RedCap). 6-items will assess learning goals of the game developed by the study team (e.g. warning signs, coping strategies, resources for support).

Concise Health Risk Tracking - Self Report

Concise Health Risk Tracking Self-Report (CHRT-SR) is a validated, 14 item, 5-point self report measures comprised of the following subscales: Propensity, Impulsivity, and Suicidal Thoughts. Responses are measured on a 5-point likert scale where 1= strongly disagree and 5= strongly agree. We will also utilize the Ask Suicide-Screening Questions (ASQ), a validated set of 4 questions to assess suicide risk.

Change in Symptoms of Anxiety

The General Anxiety Disorder-7 (GAD-7) is a validated, 7-item self report measure that assesses symptoms of anxiety. Responses are measured on a 4-point likert scale where 0=not at all and 3=nearly everyday.

Change in Symptoms of Depression

The Patient Health Questionnaire (PHQ-9) is a validated, 9-item self-report measure that assesses symptoms of depression. Responses are measured on a 4-point likert scale where 0=not at all and 3=nearly everyday.

Help-Seeking Behavior

The General Help Seeking Questionnaire (GHSQ) is a validated, 20-item self-report measure that assesses professional and non professional help seeking behaviors. Responses are measured on a 7-point likert scale where 1=extremely unlikely and 7=extremely likely.

Substance Misuse in the Past 30-Days

Substance misuse of alcohol, tobacco/vaping, cannabis, legal and illegal opioids in the past 30-days will be measured as a possible mediator. These measures are self-reported.

Suicidal thoughts and behaviors in Past 30-days – Self-Report

The Ask Suicide Screening Questions (ASQ) has used a self-reported 4-item questionnaire with youth to measure the occurrence of suicidal thoughts and behaviors. The 4 questions asked targeted a different aspect of suicidal thoughts: past wishes of death ("wish you were dead?"), suicidal ideation ("have thoughts of killing self?"), suicidal thoughts with a plan ("had a suicidal plan?"), and suicidal behavior ("tried to kill self?").

6.9 Standard Tools

N/A

7 - Statistical Analysis

7.1 Sample Size

For Content: 30 participants, including 20 high-school/college-aged youth and 10 adult providers, will make up our six focus groups. Approximately 10 interviews with adults who may have misused substances during their youth and will be able to reflect on what they wish they knew during then.

For Play Testing: 30 participants, including 10-20 high-school/college-aged youth and 10-20 adult providers, will make up our six focus groups.

For Pilot Study: 60 participants, high-school aged youth [ages 13-19], across 6-10 high schools with school-based behavioral providers.

7.2 Planned Analyses

Formative Work: Data will be analyzed using rapid analytic techniques to ensure timely analysis.^{cc} We will review field notes and focus group transcripts. We will develop a templated table to summarize each transcript.^{dd} We will then create a codebook outlining the components of safety planning to code each summary. Three team members will code each summary for researcher triangulation. We will consolidate summaries into two matrixes (adolescents and providers) to capture similar/different themes with supporting quotations. When there are discrepancies, we will discuss until full consensus. We will keep documentation of decisions, meetings, peer debriefings, and a reflexive journal as part of our audit trail to enhance the rigor and meet the trustworthiness criteria.^{ee} Data collected in the study will reside in our computerized database and electronic storage mechanisms. All data analyses will be performed under IRB approved protocols.

Pilot Study: We will assess usability, acceptability, and feasibility gathered through the use of the **User Engagement Scale- Short Form (UES-Short Form)** and **Acceptability of Intervention Measure (AIM)**. These are validated scales that will determine the reactions to the gameplay experience. We will also assess the usability, acceptability, and feasibility of the game in our post gameplay focus groups. We will also explore proximal outcomes of supported by comparing scores in intentions, coping strategies, and suicidal thoughts and associated risk factors by changes in response rating from before to after. We will also

compare scores in the severity of suicidal ideation and attempts. We will test the hypothesis that individuals who engage with supportED will report decreases in outcomes in comparison to the control group. We will conduct a longitudinal analysis using a hierarchical linear mixed model approach to compare participants in the game group to participants in the control on reported outcomes from baseline to 3-month follow-up assessments (i.e., baseline, post-gameplay, and three months). We will also use logistic regression models to determine if any relevant baseline variables are associated with changes in outcomes. We will also examine whether changes in outcomes varied by treatment group, sex at birth, sexual orientation, race, ethnicity, gameplay duration, and/or gameplay experience to determine similarities and/or differences among subgroups. **All of these analyses will be exploratory.** P-values smaller than 0.05 will be considered statistically significant.

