3.2 Hypothesis

We will test the hypothesis that individuals who engage with supportED will find the prototype engaging and acceptable (e.g., easy to use, relatable, and helpful) among youth. We will also test if the prototype is feasible to deliver in schools. We also hope to report decreases in outcomes in comparison to the control group through our exploratory findings although the sample is not large enough to correlate.

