We will collect participant demographic data including self-reported sex at birth, gender identity, sexual orientation, race, and ethnicity to determine subgroup similarities and/or differences. We will collect assessment data before and immediately after the participants engage with the game as well as at 3 months following gameplay. The primary outcomes of the proposed study are to examine: 1) the usability (e.g., ease of use) and acceptability (e.g., gameplay satisfaction) of the game among adolescents; and 2) the feasibility of delivering the game and piloting protocols in schools. To assess usability, acceptability, and feasibility, directly following supportED game completion, we will collect focus group data on participants' experiences. The following proximal outcomes, as mechanisms for behavior change, will be measured: 1) intentions to use safety plan;^r 2) coping strategies through adaptive and maladaptive subscales;^s and 3) severity of suicidal thoughts and associated risk factors using the Concise Health Risk Tracking Self-Report (CHRT-SR) comprised of the following subscales: Propensity (including domains of Pessimism, Helplessness, Limited Social Support, and Despair), Impulsivity, and Suicidal Thoughts.^t We will measure substance misuse in past 30^u days as a possible mediator. These scales will be self-reported by adolescents.

All of our data will be self-reported data; therefore, we will use data collection methods such as confidential self-administration that have been effective in our trials to minimize social desirability bias in self-reported data. Participants will receive \$25 gift cards as compensation for completion of assessments at each timepoint (e.g., baseline/post-game and 3-month follow up)

The Yale University Human Subjects Committee (the committee that reviews, approves, and monitors research on human subjects) may inspect study records. All published results will be group data. Information that will be collected during the focus group interviews will be erased 24 months after the completion of the study and after review of their content has been completed.

- 1. Formative and development work: (1 year)**

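### Section 7.2 hypothesises a decrease in every exploratory outcome, which is the wrong direction for safety-plan intentions and adaptive coping, and it leaves the outcome of the logistic models undefined

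*Combined protocol and SAP*

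**What the plan says.** The Pilot Study part of section 7.2 introduces the exploratory comparisons with "We will also explore proximal outcomes of supported by comparing scores in intentions, coping strategies, and suicidal thoughts and associated risk factors by changes", meaning change from before to after. It adds severity of suicidal ideation and attempts, and the next sentence is "We will test the hypothesis that individuals who engage with supportED will report decreases in outcomes in comparison to the control group". Section 3.2 puts the same direction as a hope, "We also hope to report decreases in outcomes in comparison to the control group", with a caveat about the sample size. I found no place that gives a direction for each outcome.

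Section 6.8 describes intentions to use a safety plan as a 7-item measure: "Responses are measured on a 5-point likert scale where 1= strongly disagree and 5= strongly agree". Sections 6.1 and 6.4 define the coping outcome as "coping strategies through adaptive and maladaptive subscales".

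Section 7.2 then plans three things: a hierarchical linear mixed model over baseline, post-gameplay and three months; logistic regression relating baseline variables to changes in outcomes; and a 0.05 threshold with no statement of sidedness. It labels all of these analyses exploratory. For Brief COPE, section 6.8 gives two visits only, baseline and 3 months.

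**The concern.** A single direction cannot suit a list that mixes outcomes meant to rise with outcomes meant to fall. Taken as written, lower intentions to use a safety plan after playing a game that models safety planning would count in favour of the game. The two coping subscales point in opposite directions, so one hypothesis cannot describe benefit on both.

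The logistic sentence raises a separate difficulty. Most of the outcomes are multi-point scores, and logistic regression needs a binary outcome. Without a named outcome, cut-off or interval, the analyst would choose these after seeing the data, against a 0.05 threshold. What is at stake is how exploratory results are read and reported.

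**Working it through.** The plan gives no figure to reproduce on this point. The first two steps compare texts. The last two are illustrations under stated assumptions.

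**1. Direction for each outcome named in 7.2**

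| Outcome | Basis in the document | Direction of benefit | Fits a decrease? |
|---|---|---|---|
| Intentions to use a safety plan | Agreement scored 1 to 5 (6.8); game models safety planning (5.1) | Increase | No |
| Adaptive coping | Subscale name (6.1, 6.4); higher anchor means more use (6.8) | Increase | No |
| Maladaptive coping | As above | Decrease | Yes |
| CHRT-SR subscales (Propensity, Impulsivity, Suicidal Thoughts) | Subscale names (6.1); agreement scored 1 to 5 (6.8) | Decrease | Yes |
| Suicidal ideation and attempts | 7.2 | Decrease | Yes |

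Intentions and the CHRT-SR carry the same agreement anchors but opposite directions of benefit, so one word cannot serve both. If the hypothesis covers only ideation and attempts, named in the sentence before it, intentions and coping have no stated direction.

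**2. Logistic models.** The dependent variable is given only as change. In 6.8, intentions, Brief COPE and CHRT-SR are Likert scores. The ASQ items, and any past-30-day use, are the natural binary candidates. Section 7.2 does not say which outcomes are meant, how a score change is split, or whether the interval ends at post-gameplay or 3 months.

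**3. What sidedness would do.** A two-sided p-value does not depend on the hypothesised direction. To show why sidedness should be stated, take 30 per arm (5.3), alpha 0.05 and an outcome that truly rises by an assumed d standard deviations. The standard error is √(2/30) = 0.258.
- One-sided test for a decrease: Φ(−d/0.258 − 1.645) = 0.25%, 0.02% and about 0% at d = 0.3, 0.5 and 0.8.
- Two-sided test: Φ(d/0.258 − 1.960) = 21%, 49% and 87%.

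**4. Precision from a common baseline mean and the sex stratum.** Assume unit variance, equal correlation r between visits, 30 per arm and complete data.
- Model with free baseline means, arm difference in change from baseline to 3 months: 2(1 − r) × 2/30 = 0.0933, 0.0667, 0.0400 at r = 0.3, 0.5, 0.7.
- Same model, plain arm difference at 3 months: 2/30 = 0.0667 at every r.
- Common baseline mean: (1 − r²) × 2/30 = 0.0607, 0.0500, 0.0340.
- Ratio for the change contrast, 2/(1 + r): 1.54, 1.33, 1.18.
- Ratio for the plain 3-month contrast, 1/(1 − r²): 1.10, 1.33, 1.96.

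The size of the gain, and its trend with r, therefore depend on which contrast is reported.

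For sex, assume a shift of 0.5 SD at both visits and equal numbers of each sex per arm. This adds 0.25 × 0.5² = 0.0625 to the variances and the covariance. The ratio of the standard error without sex to that with sex is √{[1.0625 − (r + 0.0625)²/1.0625]/(1 − r²)} = 1.016, 1.010, 1.005. It is 1.000 if sex has no effect.

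**The case against.** The best defence is that this is loose wording with no shown effect on the analysis. The hypothesis directly follows the mention of suicidal ideation and attempts, where a decrease is right. No one-sided test is planned, section 5.1 makes the purpose of the game plain, and few readers would take falling intentions as success. Item wording and any reverse scoring are not printed, so the direction of benefit is inferred. The logistic models may have been meant only for binary items.

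Most of this stands as a limit on consequence. It does not remove the need for the edit: on the narrow reading, two outcomes that 7.2 names have no direction, and the binary outcomes still have to be named.

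A reader might infer more than the documents support:
- That benefit on intentions would be tested one-sided in the wrong direction. Sidedness is not stated, so this cannot be shown.
- That the error extends to well-being, mindfulness, safety-planning knowledge and help-seeking. Section 6.8 lists them, but 7.2 does not name them under this hypothesis.
- That a definite share of information is lost by splitting scores. The plan gives no cut-off from which to compute one.
- That the mixed model is wrong at baseline. The plan does not say that the baseline means are free, and both forms are unbiased under randomisation.

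**Conclusion.** The point holds as a minor one. The stated direction is wrong for one outcome that 7.2 names (intentions) and for one subscale of another (adaptive coping, as defined in 6.1 and 6.4). The outcome of the logistic models is undefined. The first conclusion rests on the anchors, the subscale names and the stated purpose of the game.

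With two-sided tests the consequence is confined to interpretation. The primary outcomes (usability, acceptability and feasibility) are unaffected. The baseline and sex terms are an available improvement in precision, not an error in the plan, and their size rests on assumed correlations and complete data.

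**What to change.** - **Direction.** In 3.2 and 7.2, replace the single decrease with a direction for each named outcome: increase for intentions and adaptive coping; decrease for maladaptive coping, the CHRT-SR subscales and suicidal ideation and attempts. State that tests are two-sided.
- **Baseline predictors.** For score outcomes, test them with predictor × time terms in the mixed model already planned. Exclude the outcome's own baseline score as a predictor, because it is already a response in that model. Keep logistic regression for named binary items, such as ASQ responses or any past-30-day use, at a stated time point.
- **Low-cost addition.** Include sex at birth, the randomisation stratum in 5.3, as a fixed effect, chiefly because it is the stratum. Fit a common baseline mean: visit effects, with arm effects at post-gameplay and 3 months only. Name the contrast to be reported.
- **Visits.** Reconcile the two Brief COPE visits in 6.8 with the three visits in 7.2.

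The cost is a few sentences and one degree of freedom for sex. No new data are needed.

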5.2 Device Administration and Schedule

Eligible individuals will be assigned to either the 1) supportED group (n=30) or 2) control group (n=30). Both groups will also receive NIDA pamphlets on substance misuse for youth at the end of the session. Prior to receiving pamphlets, those in the supportED group will engage with the game for one session (~45min) while the control group will engage with a non-health-related game for the same duration. Given schools do not have a standardized approach to address suicide prevention, we opted to use an attention/time control condition. Participants will use a dedicated device (e.g., tablet, laptop, or desktop) to access their digital experience on the web. The research staff will be present to monitor gameplay, to provide support, if needed, and to field questions in person. Dedicated devices will be

prepped prior to sessions with participants (programmed as control or game). The school-based provider will be present for immediate referrals, if needed.

Currently our game does not record ANY personal information or even individual game information. We do not ask for a personal registration or login.

Twine by default does save information locally to the device running the Twine game off the Web server. No information is saved server-side and local information can be removed by deleting local-storage using the Web browser command to do so.

We envision most, if not all, players playing through an entire sitting in one session so saving locally shouldn't be a need, and devices will have local saves wiped if under-the-control of the research team.

We are considering disabling saves as well. However, Twine does maintain some saved state during play and it likely is cached (locally of course)

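### Section 7.2 plans logistic regression for changes in what are mostly scale scores without defining a binary or ordinal outcome, and lists two post-assignment variables among its subgroup factors

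*Combined protocol and SAP*

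**What the plan says.** Section 7.2 describes the proximal outcomes as "comparing scores in intentions, coping strategies, and suicidal thoughts and associated risk factors by changes in response rating from before to after", and adds a plan to "compare scores in the severity of suicidal ideation and attempts". A hierarchical linear mixed model compares the arms over baseline, post-gameplay and three months. For baseline predictors the text is: "We will also use logistic regression models to determine if any relevant baseline variables are associated with changes in outcomes".

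Section 6.8 lists the measures. Nearly all are multi-item scores: Brief COPE, FFMQ, S-DERS, well-being, intentions, GAD-7, PHQ-9, GHSQ and the CHRT-SR, which "is a validated, 14 item, 5-point self report measures comprised of the following subscales: Propensity, Impulsivity, and Suicidal Thoughts". A few can be coded yes/no: the four ASQ items, and recent substance use ("Substance misuse of alcohol, tobacco/vaping, cannabis, legal and illegal opioids in the past 30-days will be measured as a possible mediator").

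Section 7.2 then asks whether changes in outcomes vary by treatment group, sex at birth, sexual orientation, "race, ethnicity, gameplay duration, and/or gameplay experience to determine similarities and/or differences among subgroups". Section 6.8 places duration among the feasibility observations: "observation of modifications to conduct study, duration of gameplay, and reasons if did not finish game to end". Section 5.2 has devices set to one arm before the session, with the supportED group playing its game "while the control group will engage with a non-health-related game for the same duration". Section 5.7 restricts play to a single 45-minute session.

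**The concern.** There are two separate issues.

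**Undefined dependent variable.** Logistic regression needs a binary or ordered categorical outcome. A change in a multi-item score is neither until someone sets a cut, and the plan sets none. A cut chosen after the data are seen can be chosen for its result, and any two-way cut discards information from a sample of only 60.

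**Post-assignment subgroup factors.** Sex, race, ethnicity and sexual orientation are participant characteristics collected as demographics. Duration is observed while the participant plays the assigned game. If participants are grouped on it and the arms compared within each group, the two arms' members of a group need no longer be alike, and an arm difference can appear when the game does nothing. The same applies to gameplay experience if it means reaction to the assigned game.

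**Working it through.** The plan states no figure on this point to reproduce. From the documents come n = 60, 30 per arm (Section 5.3), and significance at 0.05 (Section 7.2; two-sided assumed). All other inputs below are assumptions.

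**1. Is a binary or ordinal change defined anywhere?** Section 7.2 speaks of change in rating. Section 6.8 gives items and response ranges but no change threshold. The moderate- and high-risk flags in Sections 4.5 and 6.4 trigger referral, and the Section 4.3 exclusion governs entry; none is a change endpoint. So there is no definition.

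**2. Cost of a two-way cut.** For a normal score cut so that a fraction q lies below the cut-point c, the information kept relative to the uncut score is φ(c)² / [q(1 − q)], where φ is the standard normal density.

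| Split | c | φ(c)² | q(1 − q) | Information kept | × 60 |
|---|---|---|---|---|---|
| 50/50 | 0 | 0.1592 | 0.25 | 0.637 | 38.2 |
| 70/30 | 0.524 | 0.1209 | 0.21 | 0.576 | 34.5 |
| 80/20 | 0.842 | 0.0784 | 0.16 | 0.490 | 29.4 |

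More categories lose less. With categories of probability p_j, the fraction kept is Σ[φ(a_j) − φ(a_{j−1})]² / p_j, where the a_j are the cut-points. This gives 0.808 for three categories at 25/50/25 (48.5 of 60) and 0.897 for five equal categories (53.8 of 60).

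**3. What that means for power.** Simulated power at n = 60, with all participants followed, for one baseline predictor with an assumed correlation to change:

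| Correlation | Linear | Ordinal, 5 categories | Binary 50/50 | Binary 80/20 |
|---|---|---|---|---|
| 0.30 | 63% | 58% | 45% | 36% |
| 0.35 | 79% | 77% | 61% | 50% |
| 0.40 | 89% | 86% | 74% | 61% |

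A check on the linear column uses the Fisher approximation Φ(atanh(r)·√57 − 1.96). At r = 0.35 it gives Φ(0.365 × 7.55 − 1.96) = Φ(0.80), or 79%.

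**4. Are the two gameplay factors baseline variables?** Duration is not, since devices are set by arm before play and duration is logged during it. For gameplay experience, usage points the same way: Section 7.2 uses the phrase for what the UES and AIM capture, and Section 6.4 for the topic of the post-game focus group. Section 6.8 lists no measure of prior gaming.

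**5. Can grouping on duration create a false arm difference?** Yes. Assume no game effect and engagement U (standard normal) that drives the outcome as 0.5U plus noise (outcome SD 1). Let duration be 40 + 3U in the game arm and 40 + U in the control arm, each with noise of SD 3. Mean duration is equal and the overall arm difference is 0.00 SD, yet the median-split groups show about +0.15 SD (long) and −0.15 SD (short). Equal mean durations therefore do not guarantee safety.

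In a simpler additive model, one arm plays 0.5 SD longer, and the trait driving duration correlates 0.3 or 0.5 with the outcome. The false difference is then about 0.10 or 0.16 SD in size. If a ceiling stops play and 80% of controls reach it, grouping on full versus short play gives about 0.06 or 0.10 SD. None of these inputs comes from the documents.

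**The case against.** Several objections have force.

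- *Logistic regression is not wrong for every outcome.* This stands. ASQ items, attempts and any past-30-day substance misuse can be modelled that way. A reader might infer that the plan uses the wrong model throughout; the documents do not support that. The fault is that Section 7.2 neither limits the method to such outcomes nor defines a change for the rest. If logistic models were used only for the binary outcomes, the information loss above would not arise.
- *The plan may never compare arms within duration groups.* This largely stands. Treatment group is itself one item in the Section 7.2 list, so each factor may simply be related to change in turn, which is ordinary exploratory work in a pilot. A reader might infer that a seriously inflated false-positive rate is built in. It is not: in the additive model, an error rate above 20% needs a 1.0 SD duration gap, a 0.5 correlation and no ceiling. The 45-minute limit and the same-duration control make that implausible. Some variation remains possible, because Section 6.8 expects to record participants who do not finish.
- *Everything here is exploratory.* This is true and keeps the severity low. Sections 5.1 and 7.2 say so, and Section 3.2 acknowledges the limits of the sample size. But Section 7.2 also sets a 0.05 significance threshold, and exploratory status does not supply a missing dependent variable.

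**Conclusion.** The first part holds: for scale scores the logistic analysis is undefined, and a better method is available within the plan's own framework. The loss from a two-way cut is roughly 36% to 51% of the information over splits from 50/50 to 80/20, assuming roughly normal change scores. The power figures further assume correlations of 0.30 to 0.40 and complete follow-up.

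The second part holds conditionally: duration, and on the documents' usage gameplay experience, arise after assignment and do not belong beside baseline subgroup factors. Bias follows only if arms are compared within groups formed on them. It is probably small, and the documents do not allow it to be sized.

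The primary usability, acceptability and feasibility outcomes are unaffected. This is a point to consider, not a threat to the trial.

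**What to change.** Amend Section 7.2 before the data are examined:

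1. For scale scores, regress the follow-up score on baseline score, arm and the baseline variable in a linear model, or add a baseline-variable by time term to the mixed model. If categories of change are wanted, define them in advance and use an ordinal model.
2. Keep logistic regression for genuinely binary outcomes (ASQ items, attempts, any past-30-day substance misuse), and state that events may be too few to model. For example, a 10% event rate gives 0.10 × 60 = 6 events, and Section 4.3 excludes actively suicidal students. Where events are too few, report counts.
3. Limit effect-modification analyses to baseline variables. Report duration and gameplay experience within arm only, labelled as non-randomised associations. Duration should come from staff-logged times, since Section 5.4 says the game will not be used to record data.
4. Optionally, include sex at birth, the randomisation stratum in Section 5.3, in the mixed model. The expected precision gain is very small: a standard error about 0.5% to 1.8% lower with baseline as covariate, if sex explains 5% to 10% of variance and the baseline–follow-up correlation is 0.5 to 0.7.

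The cost is a few sentences of analysis text, with no new assessments, plus one degree of freedom if sex is added.
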